Thus, it is proposed that subjects with DLB with amyloid copathology may have lower response to E2027 in terms of brain cGMP elevation compared to DLB subjects without amyloid copathology. This may then manifest as lower CSF cGMP in DLB subjects with amyloid copathology than DLB subjects without amyloid copathology. Furthermore, a lower brain cGMP response to E2027 in DLB subjects with amyloid copathology may lead to lower efficacy in cognitive endpoints than DLB subjects without amyloid copathology, as suggested by the trends in Study 201. As PDD and DLB are considered part of the same continuum of LBD, it is possible that subjects with PDD with and without amyloid copathology may also respond differently to E2027 treatment.

The proposed study (E2027-A001-203; Study 203) is an open-label study to evaluate the different responses to E2027 in subjects with DLB and PDD who have or do not have amyloid copathology in terms of their CSF cGMP elevation and various cognitive and neuropsychiatric endpoints. The presence of absence of amyloid copathology will be established by their plasma amyloid- β (A β)42/A β 40 ratio (as in Study 201) using the C2N Preclivity assay.

It will also evaluate the safety, tolerability, PK, and other PD effects in biomarkers of E2027 in these subjects. The relationship between CSF cGMP increase and change in efficacy endpoints will be explored. If it is found that in subjects without amyloid copathology there is greater increase in CSF cGMP, associated with improvement in efficacy endpoints, whereas in subjects with amyloid copathology there is less increase in CSF cGMP associated with worsening or no change in efficacy endpoints, then such a correlation will corroborate the results of Study 201 and support the theory that amyloid status affects E2027 drug response and downstream efficacy. The results will guide the selection of subgroups of DLB and PDD subjects (as characterized by presence or absence of amyloid copathology, or other biomarker-defined characteristics) for further evaluation of efficacy of E2027 in Phase 3 studies.

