9.3 Selection of Study Population

Approximately 64 subjects will be screened at approximately 30 investigational sites in the US and Canada to provide a maximum of 32 treated subjects, with 8 subjects in each of the 4 subgroups (DLB without amyloid copathology, DLB with amyloid copathology, PDD without amyloid copathology, and PDD with amyloid copathology). Allowing for a 25% dropout rate there will be 24 treated subjects completing the study treatment, with 6 subjects in each subgroup. Further subjects may be screened and treated with E2027 if there are less than 6 completers in any of the subgroups.

Subjects who do not meet all of the inclusion criteria or who meet any of the exclusion criteria will not be eligible to receive study drug.

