4 DETERMINATION OF SAMPLE SIZE

Assuming the standard deviation of percentage change from baseline in CSF cGMP at Week 9 was 60, the sample size of 6 completers per subgroup (for 8 enrolled subjects per subgroup, assuming a 25% dropout rate), would have approximately 80% power to detect the difference in change from baseline of CSF cGMP of 100% between the DLB without amyloid copathology subgroup and the DLB with amyloid copathology subgroup. The analysis between the PDD without amyloid copathology subgroup and the PDD with amyloid copathology subgroup, also would have approximately 80% power to detect the difference in change from baseline of CSF cGMP of 100% (same assumptions as above). These sample size calculations illustrated the possible differences that could be seen between subgroups. However, without previous data on the differences between subgroups in CSF cGMP, these were for illustration only and it was not expected statistical significance would be reached with 6 subjects per subgroup.

The probability of observing a difference in percentage of CSF cGMP between 2 subgroups (DLB without amyloid copathology subgroup minus DLB with amyloid copathology subgroup, or PDD without amyloid copathology subgroup minus PDD with amyloid copathology subgroup) $\geq 30\%$ depends on the true difference between the 2 subgroups. If the true difference was 100%, there would be 97.8% probability that the observed difference was $\geq 30\%$. If the true difference was 60%, the probability was 80.7%. If the true difference was 10%, there would be 28.2% probability that the observed difference was $\geq 30\%$.

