Summaries and figures will be produced exploring the relationships between CSF and plasma PD biomarkers and the efficacy endpoints. If data permit, the relationship between CSF and plasma PD biomarkers compared to each efficacy endpoint (MoCA, WAIS-IV DSC, CIBIC-Plus, CGIC, CFI, MMSE, NPI [NPI-12, NPI-10, NPI-4 and NPI-D, and each subscore], SAPS-PD and FAQ) and MDS-UPDRS-III will be explored using correlation analysis. The association between individual CSF/plasma biomarker concentration data and individual efficacy data within each subgroup (DLB without amyloid copathology vs DLB with amyloid copathology; PDD without amyloid copathology vs PDD with amyloid copathology; total (DLB+PDD) without amyloid vs with amyloid; DLB without amyloid vs PDD without amyloid; and DLB with amyloid vs PDD with amyloid) will be examined through scatter plots. The scatter plots including the Pearson correlation coefficient and Spearman correlation coefficient will be produced for each amyloid subgroup for both percentage change from baseline and change from baseline (as appropriate) in CSF and plasma PD biomarkers after 9 weeks of treatment and change from baseline at 12 weeks of treatment for the efficacy endpoints. Correlations against CSF and plasma biomarkers at baseline compared to change from baseline at 12 weeks of treatment for the efficacy endpoints may also be explored, by subgroups.

If appropriate, relationships amongst plasma biomarkers and CSF biomarkers (including cGMP) at baseline and after treatment will be explored using summaries, correlation analysis and scatter plots.

Pharmacogenomic Analyses

The percentage change in CSF cGMP at 9 weeks, change in CSF cGMP at 9 weeks and other CSF and plasma PD biomarkers will be summarized by ApoE4 status, using the PD Analysis Set. Other pharmacogenomic data will be summarized similarly.

Pharmacodynamic/Pharmacokinetic Analyses

The correlation amongst plasma and CSF exposure to E2027 and the various efficacy and biomarker endpoints will be explored graphically. The details will be described in the separately prepared analysis plan.

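### The cGMP-efficacy correlation is planned only in groups of about 6 or 12, with no interval; a correlation pooled within the four subgroups, with a 95% CI, should be added

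*SAP*

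**What the plan says.** Protocol 7.3 describes what would count as support: without amyloid, a larger cGMP rise accompanied by improvement; with amyloid, a smaller rise accompanied by no change or worsening. If that is seen, "then such a correlation will corroborate the results of Study 201 and support the theory that amyloid status affects E2027 drug response". The results are also meant to guide which subgroups enter Phase 3. The existing evidence for a cGMP-efficacy link is 4 subjects from the Study 201 CSF substudy (Protocol 7.2).

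SAP 5.5.2 explores the link by correlation analysis if the data allow. The specified output is this: "The scatter plots including the Pearson correlation coefficient and Spearman correlation coefficient will be produced for each amyloid subgroup". It relates Week 9 biomarker changes to Week 12 efficacy changes. The groups are the four diagnosis-by-amyloid subgroups and two pooled amyloid groups, given as "total (DLB+PDD) without amyloid vs with amyloid". No adjustment for diagnosis is named inside the pooled groups.

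The same section plans 95% CIs for the ANCOVA of cGMP but none for a correlation. It singles out no biomarker-efficacy pair and specifies no correlation over all subjects, adjusted or not.

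**The concern.** A coefficient from six subjects says little about either the size or the sign of a relationship. Shown without an interval, it can look firmer than it is. The list of outputs is also long, so there are many chances for a strong-looking value and no stated pair to look at first.

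The groups of 12 are more precise but mix DLB and PDD. If the two diagnoses differ in mean cGMP change and in mean efficacy change, a correlation can appear or vanish in the pooled group without any matching relationship within either diagnosis.

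The Protocol attaches an interpretation to this relationship and connects the results to Phase 3 planning. The trial can give a better estimate of the within-subgroup association than any one planned coefficient, at no cost in data.

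**Working it through.** **Inputs.** Protocol 9.3 gives the numbers: "Allowing for a 25% dropout rate there will be 24 treated subjects completing the study treatment, with 6 subjects in each subgroup", from screening intended "to provide a maximum of 32 treated subjects, with 8 subjects in each of the 4 subgroups". One subgroup is therefore 6 planned completers, one amyloid group is 2 x 6 = 12, and all subjects are 4 x 6 = 24 (8, 16 and 32 with no dropout). The documents give no expected correlation and no alpha for correlations, so the r values below and the two-sided 5% level are assumptions.

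**The plan's own figures first.** SAP 4 starts from "Assuming the standard deviation of percentage change from baseline in CSF cGMP at Week 9 was 60" and says that 6 per subgroup "would have approximately 80% power to detect the difference in change from baseline of CSF cGMP of 100" percentage points.
- n = 2 x (60 x 2.80/100)^2, about 5.65, rounded up to 6; 6/0.75 = 8 enrolled. Both match.
- The SE of a difference is 60 x sqrt(2/6) = 34.64. P(observed difference at least 30) is 97.8%, 80.7% and 28.2% for true differences of 100, 60 and 10. All three match.
- Power is 82.3% by the normal formula and 74.0% by a two-sided t-test. This does not bear on the present point.

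Neither document gives a precision or power figure for any correlation.

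**Precision of the planned coefficients.** The Fisher z interval is tanh(atanh(r) +/- 1.96/sqrt(n - 3)). For a correlation pooled within four subgroups, three further degrees of freedom go to the subgroup means, so the divisor is sqrt(24 - 3 - 3) = sqrt(18).

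At r = 0.6, atanh(r) = 0.693:
- n = 6: 0.693 +/- 1.96/sqrt(3) = 0.693 +/- 1.132, giving -0.41 to 0.95
- n = 12: 0.693 +/- 1.96/sqrt(9) = 0.693 +/- 0.653, giving 0.04 to 0.87
- 24 pooled within four subgroups: 0.693 +/- 1.96/sqrt(18) = 0.693 +/- 0.462, giving 0.23 to 0.82

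| Observed r | n = 6 | n = 12 | 24, pooled within four subgroups |
|---|---|---|---|
| 0.3 | -0.68 to 0.89 | -0.33 to 0.75 | -0.15 to 0.65 |
| 0.5 | -0.52 to 0.93 | -0.10 to 0.83 | 0.09 to 0.77 |
| 0.6 | -0.41 to 0.95 | 0.04 to 0.87 | 0.23 to 0.82 |
| 0.7 | -0.26 to 0.96 | 0.21 to 0.91 | 0.38 to 0.87 |

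**Information.** On the z scale it is 3, 9 and 18. The pooled estimate therefore has 18/3 = 6 times the information of one subgroup and 18/9 = 2 times that of one amyloid group.

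**Smallest |r| distinguishable from zero at 5%.** With t/sqrt(t^2 + df) and df of 4, 10 and 19, it is 0.81, 0.58 and 0.43. If the true r were 0.5, the chance of reaching it (simulation, bivariate normal) is 17%, 40% and 67%.

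**How easily a strong-looking value arises.** With no true correlation, P(|r| at least 0.7) at n = 6 is 0.1215. For a single biomarker-efficacy pair, the chance that at least one of four subgroups shows it is 1 - (1 - 0.1215)^4 = 40%. Reading the NPI subscores as its 12 items, SAP 5.5.2 lists 25 clinical measures: MoCA, WAIS-IV DSC, CIBIC-Plus, CGIC, CFI, MMSE, four NPI summary scores, 12 NPI items, SAPS-PD, FAQ and MDS-UPDRS-III.

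**Other ways to combine, at r = 0.5.** A crude correlation over 24 gives 0.12 to 0.75 but mixes within-group and between-group effects. Averaging four subgroup z values (information 4 x 3 = 12) gives -0.02 to 0.81, less precise than the pooled within-subgroup estimate. The method therefore needs to be named.

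**If all 32 are evaluable, at r = 0.5.** n = 8 gives -0.32 to 0.89, n = 16 gives 0.01 to 0.80, and 32 pooled within subgroups gives 0.16 to 0.73. The ordering is unchanged.

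**The case against.** The strongest reply is that the Section 7.3 pattern is in large part a contrast between amyloid groups. A correlation adjusted for the four subgroups removes that contrast. If amyloid status drove both cGMP and efficacy, with no residual association within groups, the sponsor's hypothesis would be true and the adjusted correlation would be expected to be zero. Conversely, a strong within-subgroup correlation could occur with no amyloid difference. This stands. A reader might infer that the Section 7.3 statement should rest on the adjusted correlation; the documents do not support that. The between-group part already has ANCOVA differences with 95% CIs (SAP 5.5.2) and efficacy summaries by subgroup (SAP 5.8). What remains without an interval is the association itself.

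Second, the analysis is exploratory. It is conditional on the data, no formal tests of efficacy are planned (SAP 5.8), and SAP 5.3.4 promises caution with small subgroups. This also stands. It rules out calling the correlation the trial's main conclusion. A reader might also multiply 25 measures by four subgroups and predict about 5 of 100 coefficients beyond 0.81 by chance. That applies a significance threshold the SAP never proposes. A general promise of caution is still weaker than an interval beside the coefficient.

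Third, the planned plots together show every evaluable subject, DLB and PDD are also plotted separately, and the opening sentence on correlation analysis does not exclude an overall estimate. The table shells and the separate PK/PD plan are not available and may add detail. All true, so it would be too strong to say that data are discarded or a pooled estimate is ruled out. It is simply not specified.

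Finally, MoCA is a choice: Protocol 7.2 and 9.2 cite both MoCA and CIBIC-Plus. MoCA is reasonable because it gave the near-significant Study 201 subgroup result, defines the FAS and is repeated across the further subgroups in SAP 5.8.

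**Conclusion.** The point holds as a low-cost improvement to an exploratory analysis. As specified, the cGMP-efficacy association would be read from coefficients too imprecise to interpret alone at n = 6, and unadjusted for diagnosis at n = 12. The gain from pooling within subgroups is sixfold over one subgroup and twofold over one amyloid group.

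This rests on 24 planned completers, roughly bivariate-normal data and a similar slope in all subgroups. Exclusion of low-compliance subjects from the PD Analysis Set (SAP 5.2.1) or missing Week 12 scores would reduce the numbers. Six subjects per subgroup can check the common slope only roughly. Even pooled, an observed 0.6 is compatible with a true value from 0.23 to 0.82, so the result stays exploratory.

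**What to change.** Add to SAP 5.5.2, labelled supplementary and exploratory:
- A partial correlation of Week 9 percentage change in CSF cGMP with Week 12 change in MoCA, over all evaluable subjects in the PD Analysis Set, adjusted for the four diagnosis-by-amyloid subgroups, with a 95% CI. Name the method (Fisher z with the adjusted degrees of freedom), because the alternatives differ in precision.
- 95% CIs on the planned subgroup coefficients for this pair, with the interval method for Spearman stated.
- A sentence saying that the Section 7.3 pattern will be read from the between-amyloid contrasts (ANCOVA of cGMP and efficacy summaries) and the within-subgroup association together, and that the adjusted correlation assumes a common slope.

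Keep the subgroup plots, the ANCOVA and the efficacy summaries as they are. The cost is a few lines of SAP text and one extra table, with no new data.

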5.6 Safety Analyses

Evaluations of safety will be performed on the Safety Analysis Set. The incidence of AEs, out-of-normal-range laboratory safety test variables, abnormal ECG findings, and out-of-range vital signs, suicidality (C-SSRS), MDS-UPDRS-III, along with change from baseline in laboratory safety test variables, ECGs, and vital sign measurements (including orthostatic changes) will be summarized by subgroup and overall.

Study Day 1 for all safety analyses is defined as the date of the first dose of study drug.

5.6.1 Extent of Exposure

Extent of exposure will be summarized by categories of cumulative weeks as well as by categories of duration of exposure. The number and percent of subjects for each exposure category will be presented by subgroup and overall. Duration of exposure is the number of days between the date the subject received the first dose of study drug and the date the subject received the last dose of study drug and will be summarized using descriptive statistics for continuous variable by subgroup and overall. Overall exposure (number of subject-weeks) is defined as summation over all subjects' exposure durations and will be summarized by subgroup and overall.

5.6.2 Adverse Events

The AE verbatim descriptions (investigator terms from the CRF) will be classified into standardized medical terminology using the MedDRA. Adverse events will be coded to the MedDRA (Version 21.0 or higher) LLT closest to the verbatim term. The linked MedDRA PT and primary SOC will also be captured in the database.

A TEAE is defined as an AE that emerged during treatment or within 28 days following the last dose of study drug, having been absent at pretreatment (Baseline) or

- Reemerged during treatment, having been present at pretreatment (Baseline) but stopped before treatment, or
- Worsened in severity during treatment relative to the pretreatment state, when the AE was continuous.

Only those AEs that are treatment emergent will be included in summary tables. All AEs, treatment emergent or otherwise, will be presented in subject data listings.

Treatment-emergent AEs (TEAEs) will be summarized by subgroup and overall, on the Safety Analysis Set. The incidence of TEAEs will be reported as the number (percentage) of subjects with TEAEs by SOC and PT. A subject will be counted only once within a SOC and PT, even if the subject experienced more than one TEAE within a specific SOC and PT. The number (percentage) of subjects with TEAEs will also be summarized by maximum

severity (mild, moderate, or severe). The number (percentage) of subjects with TEAEs will also be summarized by relationship to study drug (related and not related).

Summaries of common TEAEs will be produced.

A subject data listing of all AEs leading to death will be provided.

The number (percentage) of subjects with treatment-emergent serious adverse events (SAEs) will be summarized by MedDRA SOC and PT for each subgroup and overall. A subject data listing of all SAEs will be provided.

The number (percentage) of subjects with TEAEs leading to discontinuation from study drug will be summarized by MedDRA SOC and PT for each subgroup and overall. A subject data listing of all AEs leading to discontinuation from study drug will be provided.

TEAEs associated with special situations such as overdose, misuse, abuse, medication error, pregnancy, TEAEs with signal of possible drug abuse potential, and those requiring additional Medical Monitor follow-up will be listed and summarized similarly.

A summary of non-treatment emergent AEs will be produced, these are AEs which occurred >28 days after final dose of study drug.

5.6.3 Laboratory Values

Laboratory results will be summarized using Système International (SI) units, as appropriate. For all quantitative parameters listed in protocol Section 9.5.1.4.4. Safety Assessments (Laboratory Measurements), the actual value and the change from baseline to each post-baseline visit and to the end of treatment (defined as the last on-treatment value) will be summarized by visit, subgroup and overall, using descriptive statistics. Qualitative parameters listed in protocol Section 9.5.1.4.4 will be summarized using frequencies (number and percentage of subjects), and changes from baseline to each postbaseline visit and to end of treatment will be reported using shift tables. Percentages will be based on the number of subjects with both non-missing baseline and relevant post-baseline results.

Laboratory test results will be assigned a low/normal/high (LNH) classification according to whether the value was below (L), within (N), or above (H) the laboratory parameter's reference range. Within subgroup comparisons for each laboratory parameter will be based on 3-by-3 shift table that compares the baseline LNH classification to the LNH classification at each post-baseline visit and at the end of treatment. Similar shift tables will be used to compare the baseline LNH classification to the LNH classification for the highest and lowest value during the treatment period.

The Sponsor's Grading for Laboratory Values (see Appendix 13.1) presents the criteria that will be used to identify subjects with TEMAV. Except for phosphate, a laboratory value was determined to be a treatment-emergent markedly abnormal value (TEMAV) if the post-baseline grade increased from baseline and the post-baseline grade was greater than or equal to 2. For phosphate, a laboratory value was determined to be a treatment-emergent markedly

abnormal value (TEMAV) if the post-baseline grade increased from baseline and the post-baseline grade was greater than or equal to 3. When displaying the incidence of TEMAUs, each subject will be counted once in the laboratory parameter high and in the laboratory parameter low categories, as applicable.

5.6.4 Vital Signs

Descriptive statistics for vital signs parameters (diastolic blood pressure [DBP] and systolic blood pressure [SBP], heart rate [HR], respiration rate, temperature and weight) and changes from baseline for above parameters as well as orthostatic changes for diastolic and systolic blood pressure, pulse will be presented by visit and subgroup and overall.

Orthostatic hypotension is defined based on the following criteria per protocol:

Drop in standing SBP ≥ 20 mmHg compared to supine, or drop in standing DBP ≥ 10 mmHg compared to supine.

Treatment-emergent orthostatic hypotension means if at baseline subject did not have SBP drop ≥ 20 and no DBP drop ≥ 10 compared to supine, but developed one or more of these two events during postbaseline visits.

Orthostatic tachycardia by numerical criteria is defined by the following numerical criteria:

Standing HR increases by >30 beats/min compared to supine AND absolute standing HR is >100 beats/min.

Orthostatic tachycardia without orthostatic hypotension will be considered a true orthostatic tachycardia and an instance of treatment emergent true orthostatic tachycardia is defined below:

1. Orthostatic tachycardia by above numerical criteria
2. No orthostatic hypotension (ie, neither standing SBP drop by >20 nor standing DBP drop >10 compared to supine) at the same time point.
3. Does not meet criteria #1 and #2 at Baseline.

Additionally, instances of orthostatic hypotension by numerical criteria and treatment-emergent orthostatic hypotension, and instances of orthostatic tachycardia by numerical criteria and treatment-emergent true orthostatic tachycardia will be summarized by subgroup and overall and visit.

Listing of vital signs including orthostatic changes will be provided.

In addition, the number (percentage) of subjects with clinically notable vital signs will be summarized by subgroup and overall. Table 2 presents the clinical notable ranges.

Table 2 Clinical Notable Ranges for Vital Signs

Vital Sign	Criterion for Low	Criterion for High
Pulse (bpm)	< 50	> 100
Temperature (°C)	< 36	> 38
Weight (kg)	< 45	> 100
Systolic BP	< 90	> 160
Diastolic BP	< 60	> 100

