9.5.1.4.5 VITAL SIGNS AND WEIGHT MEASUREMENTS

Vital sign measurements (ie, systolic blood pressure [BP] and diastolic BP [mmHg] including orthostatic evaluations, pulse [beats per minute], respiratory rate [per minute], body temperature [in centigrade]), height (m), and weight (kg) will be obtained at the visits designated in the Schedule of Procedures/Assessments (Table 5) by a validated method. Blood pressure and pulse will be measured after the subject has been resting for 10 minutes in the supine position. Blood pressure and pulse will be measured again after standing up for 2 minutes. All BP measurements should be performed on the same arm, preferably by the same person.

When vital signs are to be obtained on the same day as PK or other blood samples, the vital sign measurements will be performed prior to drawing blood samples in order to maximize the accuracy of blood sampling times while minimizing the potential effects of blood drawing on recordings obtained during safety assessments.

Orthostatic (postural) hypotension will be defined as either asymptomatic orthostatic hypotension (change in BP upon standing without lightheadedness) or symptomatic orthostatic hypotension (change in BP upon standing accompanied by lightheadedness).

Orthostatic hypotension will be recorded based on the following criteria:

- Drop in systolic BP ≥ 20 mmHg, or
- Drop in diastolic BP ≥ 10 mmHg

Occurrences of orthostatic hypotension as defined above that also meet any of the following criteria are considered clinically significant and will be reported as AEs in this study:

- Postural lightheadedness noted upon standing (ie, symptomatic orthostatic hypotension)
- Requires intervention (eg, resumption of recumbent position, IV fluids, etc.)

Postural lightheadedness upon standing if accompanied by orthostatic BP changes meeting the above criteria of orthostatic hypotension should be reported as AE of orthostatic hypotension.

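### SAP 5.6.4: the no-hypotension condition for treatment-emergent true orthostatic tachycardia uses strict limits (>20, >10), which is not the complement of the inclusive definition (≥20 or ≥10) used elsewhere

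*SAP*

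**What the plan says.** Protocol 9.5.1.4.5 gives inclusive limits for orthostatic hypotension. The systolic limit reads "Drop in systolic BP ≥ 20 mmHg, or" and the diastolic limit reads "Drop in diastolic BP ≥ 10 mmHg". SAP 5.6.4 adopts these limits, "Drop in standing SBP ≥ 20 mmHg compared to supine, or drop in standing DBP ≥ 10 mmHg compared to supine", and its lead-in names the protocol as their source ("Orthostatic hypotension is defined based on the following criteria per protocol"). The baseline condition for treatment-emergent hypotension in that section is inclusive too: "at baseline subject did not have SBP drop ≥ 20 and no DBP drop ≥ 10 compared to supine".

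SAP 5.6.4 then defines orthostatic tachycardia numerically as a heart-rate rise above 30 beats/min with a standing rate above 100 beats/min. The protocol has no numerical definition of its own. The SAP adds a refinement: "Orthostatic tachycardia without orthostatic hypotension will be considered a true orthostatic tachycardia". The treatment-emergent form has three criteria:

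1. The heart-rate criteria are met.
2. There is no orthostatic hypotension at the same time point, glossed as "neither standing SBP drop by >20 nor standing DBP drop >10 compared to supine".
3. Criteria 1 and 2 are not both met at baseline.

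Four results are tabulated by subgroup, overall and visit: hypotension by numerical criteria, treatment-emergent hypotension, tachycardia by numerical criteria, and treatment-emergent true tachycardia.

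**The concern.** The true category exists to separate tachycardia that comes with a fall in pressure from tachycardia that does not. At a single time point a record must fall on one side or the other. The definition and the gloss in criterion 2 disagree when a drop sits exactly on a limit, and neither document gives a tie rule.

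The incidence of orthostatic hypotension and orthostatic tachycardia is a named secondary endpoint (Protocol 9.7.1.1.2, SAP 5.1.2), and safety and tolerability is the only secondary objective. Two programmers reading the section could code criterion 2 differently, one from the defined term and one from the numbers in parentheses. With a planned 8 subjects per subgroup, a difference of one subject would be visible in the table.

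**Working it through.** This is a check of logic. The plan gives no figure to reproduce.

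**Step 1: the two rules.** Let S and D be the systolic and diastolic drops (supine minus standing, mmHg).

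- Hypotension (Protocol 9.5.1.4.5, SAP 5.6.4): S ≥ 20 or D ≥ 10.
- No hypotension, from the gloss in criterion 2: S ≤ 20 and D ≤ 10.

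The complement of the first rule is S < 20 and D < 10, so the two rules overlap.

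**Step 2: the overlap.** Both rules hold when S = 20 with D ≤ 10, or D = 10 with S ≤ 20.

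| S, D | Hypotension by definition | Passes criterion 2 gloss | Conflict |
|---|---|---|---|
| 19, 9 | no | yes | no |
| 20, 5 | yes | yes | yes |
| 15, 10 | yes | yes | yes |
| 20, 10 | yes | yes | yes |
| 20, 15 | yes | no | no |
| 25, 10 | yes | no | no |

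On a whole-number grid with S from 0 to 40 and D from 0 to 30, S = 20 gives 11 conflicting pairs and D = 10 gives 21. The pair (20, 10) is shared, so the total is 11 + 21 − 1 = 31. That count describes the grid and is not a rate. There is no gap in the other direction: any record failing criterion 2 has S > 20 or D > 10 and so meets the definition. With criterion 2 set to S < 20 and D < 10, the count falls to 0.

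**Step 3: what reaches a table.** A conflicting record enters the true-tachycardia count only if the heart rate also rises by more than 30 and exceeds 100 standing, and criterion 3 is satisfied. After baseline, such a record adds a case. At baseline, it is taken as pre-existing true tachycardia and stops a later genuine case from counting as treatment-emergent. The two effects pull in opposite directions.

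**Step 4: order of magnitude.** The documents give no distribution of orthostatic drops and no digit-recording practice, so everything here is assumed: S normal with mean 5 to 10 and SD 12 to 15, D normal with mean 2 to 4 and SD 7 to 9, S and D independent. With F the normal distribution function and h half the recording unit (0.5 for 1 mmHg, 1 for 2 mmHg):

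P(conflict) = F_S(20 + h) × F_D(10 + h) − F_S(20 − h) × F_D(10 − h)

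- Lowest (means 5 and 2, SDs 15 and 9, h = 0.5): 0.8493 × 0.8275 − 0.8331 × 0.7977 = 0.038.
- Highest (means 10 and 4, SDs 12 and 7, h = 1): 0.8203 × 0.8413 − 0.7734 × 0.7625 = 0.10.

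Over the full set of assumptions this is about 4–5% of records with 1 mmHg recording and 8–10% with even digits, before the heart-rate criteria.

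Protocol Table 5 schedules vital signs at five post-baseline visits (Weeks 3, 6, 9, 12 and follow-up), so 32 planned subjects give at most 32 × 5 = 160 scheduled records. Assume also that 1% to 5% of records meet both heart-rate criteria, independently of the drop:

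- Low: 160 × 0.038 × 0.01 = 0.06 records.
- High: 160 × 0.10 × 0.05 = 0.80 records.

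At baseline the corresponding range is 32 × 0.038 × 0.01 = 0.01 to 32 × 0.10 × 0.05 = 0.16 records, and these matter only if the same subject later has true tachycardia. If tachycardia tends to accompany a fall in pressure, independence understates these figures.

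**The case against.** The best defence is that criterion 2 names orthostatic hypotension, a term already defined in the section, and the sentence before it repeats the idea. On that reading the parenthesis is a loose gloss and the defined term governs. The derivation rules sit in separate programming specifications (SAP 9), so coding from the gloss is a possibility and not a certainty. The orthostatic changes are also listed, so a boundary record would stay visible. All of this stands, and it makes a slip between > and ≥ the likely explanation. It does not settle the rule, because the parenthesis is where the numbers for this criterion appear.

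The signs might have lost an underline in typesetting. That cannot be shown, and ≥ appears correctly in the hypotension definition and in its treatment-emergent form in the same section.

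A reader might infer more than the documents support:

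- **That the whole secondary endpoint is miscounted.** Three of the four tabulated results do not use criterion 2. Adverse events of orthostatic hypotension follow separate reporting rules in Protocol 9.5.1.4.5.
- **That every drop of exactly 20 or 10 is double-classified.** Pairs such as (20, 15) and (25, 10) are hypotension under both rules.
- **That no subject may appear in both tables.** Exclusivity applies at one time point. A subject can properly contribute to each from different visits.
- **That true tachycardia is overstated.** Criterion 3 can remove cases as well.
- **That the error is worth 12.5 percentage points.** That is 1/8, the weight of one subject in a planned subgroup, and not an expected effect.

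**Conclusion.** The inconsistency is real and lies within one SAP section. As written, criterion 2 is not the complement of the hypotension definition that the SAP takes from the protocol, and nothing elsewhere resolves it. The consequence is confined to the treatment-emergent true orthostatic tachycardia summary, a descriptive safety result, and its net direction is undetermined.

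The logical part rests only on the text. The size rests on the assumed distributions and heart-rate share: roughly 0.06 to 0.8 post-baseline records in the whole study, so possibly none. It is a minor correction, worth making because the rule drives a tabulated result.

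**What to change.** In SAP 5.6.4, reconcile criterion 2 with the definition already in the SAP and protocol. Either require that the record does not meet the orthostatic hypotension definition given above, or state the complement directly: neither a standing systolic drop ≥20 mmHg nor a standing diastolic drop ≥10 mmHg compared with supine. Referring back to the definition is safer, because one set of limits then serves the whole section.

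Criterion 3 reuses criterion 2 and is corrected with it. The programming specifications should be checked for the same signs.

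The cost is two symbols, or one cross-reference, and a matching line of code. No data collection changes. The edit concerns how records are classified for analysis; it proposes no clinical threshold and does not touch subject management.
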